Appendix III. Drug Management Protocol

INVESTIGATIONAL DRUG MANAGEMENT PROTOCOL:

The following outlines procedures for study drug management under the direction of the Principal Investigators, Drs. [name], [name].

Study Title: Psilocybin-assisted cognitive behavioral therapy for major depressive disorder.

IRB#: 21-002134

IND#: 160212

A. Ordering and Receipt:

1. [name], holder of the Schedule I drug research license, will place the order for psilocybin from Psilo Scientific Ltd. (Vancouver, B.C., Canada).
2. A record of the request for investigational drugs from the manufacturers will be kept in the study's file as reference
3. Study drugs will be sent to [name]. The shipment will be received by [name] along with an approved individual listed on the license as a witness.
4. When the study drug is received, the product will be checked to verify accuracy of the shipment as compared to what was requested for:
 - a. Integrity of the study drug for any breakage or inappropriate temperature
 - b. The drug, strength, dosage and quantity
5. Any irregularities observed will be reported to the manufacturer
6. The drug shipment receipts will be recorded into the appropriate drug accountability record form documenting the following (Drug Master Log)
 - a. Date of receipt (date, month, year)
 - b. Study drug supplier
 - c. Dosage form and amount received.
 - d. Drug lot number
 - e. Recorder's initial and date of recording.
7. Inventory will be confirmed by an additional approved individual listed on the license who will also sign and date the drug accountability form.
8. Psilocybin will immediately be stored in the [name] DEA-approved Schedule I study drug facility under conditions consistent with those recommended by the manufacturer.

B. Storage

1. Psilocybin will be stored under conditions consistent with those recommended by the manufacturer, in a secure location only accessible to the Principal Investigators and authorized designees. A delegation of authority list will identify individuals authorized to have access to the study drugs.
2. Psilocybin will not be stored with other non-study drug products. The storage container (drug safe) will be labeled with "investigational and study drug" and the IRB study number.
3. The security management for Schedule 1 drug storage will follow the protocol approved by the DEA.
4. Investigational and study drug agents will be clearly labeled with:
 - a. Name of the drug
 - b. IRB protocol number
 - c. Name of the Principal Investigator
 - d. "Investigational and study drug use only" designation
 - e. Drug doses: 10 mg psilocybin or 25 mg psilocybin (per capsule)

C. Accountability

1. A complete and accurate system for psilocybin will be maintained
2. The inventory record will document each transaction from receipt and storage to dispensing or disposal of the drug.
3. For each transaction, the following information will be recorded:
 - a. The date (day/month/year)
 - b. Destination of drug transfers or returns
 - c. Participant's study ID number, session number, and date of dispensing
 - d. Dose dispensed
 - e. Initials of the person completing the inventory record
 - f. A copy of the signed informed consent form for the protocol and prescription will be included in the participant's study record. The maintenance of this information is the direct responsibility of the investigator.
 - g. The protocol and basic information concerning the pharmacology, dosage, preparation, administration, adverse effects of the study drugs will be readily available in a protocol-specific central laboratory binder that is maintained on site and readily available for review. This laboratory binder will include the name and method of contact for the investigator and study physician responsible for handling any problems or emergencies that occur. The provision of this information is the direct responsibility of the investigator.
4. Inventory logs
 - a. The Usage Inventory Log will show: Batch information (purchase order, date of receipt, individuals who received drug), Drug information (substance and dosages). Underneath the header information previously listed will be the following dispensing information: Individual doses dispensed to participants, Date of dispensing, remaining balance, study psychiatrist dispensing substance, and participant number, session number and date
 - i. This is a single-blinded study, researchers will be aware of the psilocybin dispensed to participants.
5. Any discrepancies in accountability that cannot be rectified (i.e., missing drug) will immediately be reported to the DEA.
6. At the end of the study, unused doses will be destroyed or sent to a reverse distributor with a Schedule I license for destruction.

D. Dispensing

General dispensing and administration procedures:

1. Once a participant is enrolled in the study, a study physician designated by [name] DEA license, will prepare an investigational drug prescription for psilocybin. The prescription will include the following:
 - a. Date and protocol number
 - b. The full name (first and last name) of the participant, date of birth, known allergies
 - c. The subject's study ID and session number (1-4)
 - d. The identity of the study drug and strength (10mg or 25 mg psilocybin), route of administration, (oral), and "no refills."
 [name] (Schedule I license holder) will be a co-signer on prescriptions.
2. Two copies of the prescription will be made for keeping in the participant's study file and the original prescription will be filed, chronologically in the study drug room after dispensing with drug inventory logs in the Schedule I storage location labeled with the IRB #, IND #, and study drug.

3. The study drug will be transported by authorized personnel on [name] DEA license from the storage location in the UCLA Semel Institute to the drug session room (also within the UCLA Semel Institute) in a zippered medication bag. This location will be added to [name] I registration.
4. The subject will be observed taking the study drug(s) as prescribed by the study physician.
5. The investigator will verify that the dose was administered on the study session checklist with initials, time of administration, and date and on the log verifying that a dose was dispensed.

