The two drug administrations will be conducted with one individual participant at a time, each done in a single day. The first drug session (10mg dose) will be conducted over a 6-hour period and the second, high dose session (25mg) will be conducted over an 8-hour period. The first drug administration will be conducted following the third CBT session; the second will be conducted following the sixth session. Participants will be instructed to eat a light, low-fat breakfast on the day of the drug session and to arrive at the study site at 8am.

When the participant arrives at the UCLA Semel Institute for the drug session, prior to the psilocybin's administration, the participant will conduct a urine screen to test for the presence of and illicit drugs and, if the participant is biologically female, to confirm that she is not pregnant. Prior to the psilocybin's administration, participants will also be assessed for recent alcohol use through a breathalyzer test. Participants must have negative toxicology and pregnancy (if applicable) screens as well as no detectable amount of alcohol as measured by the breathalyzer test (i.e., 0.00% BAC) in order to proceed with the drug session. Participants who test positive for any illicit drugs, pregnancy, or alcohol will at any of the study screenings will not be allowed to proceed with the drug session and will be removed from the study. Participants will then be re-oriented to the plan for the day, including that they will be taking psilocybin and remaining in the therapy room for the duration of the drug experience (with the exception of bathroom breaks, as needed). The participant will then be given the psilocybin (10mg [administered in two 5mg capsules] for the first administration; 25mg [administered in one capsule] for the second administration) with a glass of water to begin the drug session. The results of the drug and pregnancy screens, administration of study drug(s), and safety measurements throughout the psilocybin session (see below) will all be catalogued on the study's case report form, which is shown in Appendix I (pg. 25).

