The psilocybin will be produced according to GMP regulations by Psilo Scientific Ltd. (a wholly-owned subsidiary of Filament Health Corp.; [name]) under their Schedule I license. Stability and purity are verified with a Certificate of Analysis. A letter of authorization from Psilo Scientific Ltd. to reference their Drug Master Files (DMF #035999 (DS) and #036004 (DP)) has been submitted to the FDA for IND for the study. Psilocybin (Schedule I) will be stored in [name] I highly secured storage facility in the UCLA Semel Institute under [name] DEA license.

Operating Procedures

The operating procedures for receiving, storing, dispensing, and transporting the drug are outlined here. See the full details of the Drug Management Protocol in Appendix III (pg. 29-31) as well as the security provisions for drug storage in Appendix IV (pg. 32). In summary, the psilocybin will be received by [name] (along with an authorized personnel on [name] DEA Schedule I license as witness) – shipped to [name] laboratory at UCLA Semel Institute from Psilo Scientific Ltd. Immediately upon receipt, the psilocybin will be checked to ensure correct product and quantities received. The drug and quantities will be recorded into inventory in the study's drug log, signed by authorized personnel and locked in [name] DEA approved storage location (see attached UCLA Controlled Substances Program Usage Log in Appendix V; pgs. 33-34).

The study drugs will be prescribed by a study physician with appropriate DEA authorization. Prior to a psilocybin drug session, the appropriate dose of psilocybin will be prepared. The drug will be placed in a plastic Ziplock bag and labeled with the drug's name and dose. The study drug log will be updated by a DEA authorized study personnel to indicate the drugs dispensed. The study drug will be transported by a DEA authorized personnel from [name] DEA-approved storage location on the A floor of the UCLA Semel Institute to the drug session room (also on the A-floor of the UCLA Semel Institute) in a zippered medication bag. The subject will be given the study drug to self-administer and will be observed taking the study drug as prescribed by the study physician.

LABORATORY FACILITY:

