Any participant who is withdrawn from the study for any of the above exclusionary criteria will be referred to treatment elsewhere. For participants who have begun CBT, they will be retained in the study protocol (but not allowed to participate in forthcoming psilocybin sessions) for as long as possible, or until the CBT has ended.

Adverse drug reaction. Participants will be withdrawn from the study if they have an overwhelmingly distressing response to the first, low dose drug session. An overwhelmingly distressing response is considered one that requires hospitalization due to acute unmanageable psychosis, psychological distress, or a hypertensive crisis (i.e., blood pressure at or exceeding 180 systolic and 120 diastolic mmHg); use of rescue medication due to acute psychosis, psychological distress/anxiety, or elevated blood pressure (i.e., blood pressure exceeding 160 systolic and 100 diastolic mmHg); or otherwise is determined by study staff that the participant cannot be kept safe on a higher dose of the drug. Additionally, participants will be withdrawn from the study if they have an allergic reaction (e.g., swelling, itching) caused by the psilocybin or any persisting headaches or visual-perceptual effects that are distressing or interfering and lasting longer than two days after the first psilocybin administration. The participant will be referred to treatment elsewhere but will be retained in the study protocol for as long as possible or until the CBT has ended. Any participant with an adverse drug reaction to the second psilocybin administration will be offered continued support via the study's outlined CBT protocol.

These circumstances that may require administrative withdrawal will be spelled out in the consent

forms. Despite being withdrawn from study interventions, we will attempt to retain these participants for study assessments with their consent.

Participant worsening or non-response

Each participant will be seen weekly by their study therapist for two months following their first psilocybin session and one month following their second psilocybin session. Participants will continue to engage in biweekly therapy for the next month. Participants will then undergo a study assessment within two weeks of their treatment termination and another three months following treatment termination. At each of these visits, subjects' depressive symptoms (including suicidality) and functioning will be monitored.

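### The 10 mg first dose is described as two 5 mg capsules in the main text, but Appendix III, read naturally, labels low-dose capsules as 10 mg each, and nothing in the plan settles which is right

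*Combined protocol and SAP*

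**What the plan says.** The administration paragraph of the General Investigational Plan gives both the number and the strength of the low-dose capsules: "10mg [administered in two 5mg capsules] for the first administration; 25mg [administered in one capsule] for the second administration".

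Appendix III (Drug Management Protocol), section B, item 4e, sets what the study drug label must carry: "Drug doses: 10 mg psilocybin or 25 mg psilocybin (per capsule". It names no 5 mg unit.

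Appendix III, item D.1d, lists what the prescription must contain: "The identity of the study drug and strength (10mg or 25 mg psilocybin), route of administration, (oral", together with a no-refills statement. No number of capsules is listed.

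The low-dose session also serves a safety purpose. Under Participant Monitoring and Removal from the Study (Adverse drug reaction): "Participants will be withdrawn from the study if they have an overwhelmingly distressing response to the first, low dose drug session". The grounds include a judgement by staff that the participant could not be kept safe on a higher dose.

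Several checks surround dispensing:

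- At receipt, the shipment is compared with the order for "The drug, strength, dosage and quantity" (Appendix III, A.4b).
- Before a session, "The drug will be placed in a plastic Ziplock bag and labeled with the drug's name and dose" (Study Drugs, Operating Procedures).
- The prescription is co-signed (D.1), the dose dispensed and a running balance are logged (C.3d, C.4a), and "The subject will be observed taking the study drug(s) as prescribed by the study physician" (D.4).

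**The concern.** Two operative instructions describe the same physical item, the low-dose capsule, and they give different strengths. The 25 mg capsule agrees in both places, so the conflict is confined to the first session.

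If the supplied capsules hold 5 mg, B.4e as naturally read puts a label of twice the true strength on a Schedule I investigational drug. If they hold 10 mg, following the main text's two-capsule instruction would double the first dose.

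What is at stake is the meaning of the low-dose step. A participant goes on to 25 mg partly because 10 mg was tolerated. That inference depends on 10 mg having been given.

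**Working it through.** **Inputs**

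- Planned doses: 10 mg, then 25 mg (Specific Aims; General Investigational Plan).
- Low-dose make-up in the main text: 2 capsules of 5 mg.
- Low-dose capsule strength in Appendix III B.4e, read naturally: 10 mg.
- High-dose make-up: 1 capsule of 25 mg, consistent in both places.

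**Formula:** dose given = number of capsules × mg per capsule.

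**Each instruction taken alone reproduces the planned first dose**

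- Main text: 2 × 5 = 10 mg.
- Appendix III: 1 × 10 = 10 mg.

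**The two set against each other**

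- Labelled strength against main-text strength: 10 / 5 = 2.

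**If the two are crossed at dispensing**

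| Case | Dose given | Relative to 10 mg | Step up to 25 mg |
|---|---|---|---|
| As planned | 10 mg | 1 | 25 / 10 = 2.5-fold |
| Two capsules, each truly 10 mg | 2 × 10 = 20 mg | 20 / 10 = 2 | 25 / 20 = 1.25-fold |
| One 5 mg capsule labelled 10 mg | 1 × 5 = 5 mg | 5 / 10 = 0.5 | 25 / 5 = 5-fold |

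The 20 mg case is 20 / 25 = 80% of the high dose and 25 − 20 = 5 mg below it, so it stays under the planned maximum. The 5 mg case errs the other way: a participant could pass the tolerance step on half the intended dose and then face a larger jump.

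**Does any other text settle the strength?**

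- *Prescription (D.1d):* a stated strength of 10 mg with no count fits either make-up.
- *Bag label (Study Drugs):* drug name and dose only.
- *Accountability record (C.3d):* dose dispensed, with no unit strength.
- *Case report form (Appendix I):* identifies session 1 as 10 mg; no capsule count appears in the legible fields.
- *Receipt check (A.4b):* compares the shipment with the order, so it passes whichever strength was ordered. The ordered strength is not stated.
- *Observed dosing (D.4):* confirms that the participant took what was dispensed, not that the capsule count suited the strength.
- *Running balance (C.4a):* could expose a wrong count, but only after dispensing.

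All of these agree on a 10 mg total. None says what one low-dose capsule contains.

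**The case against.** The strongest reply is that the documents do not prove either instruction wrong. Item B.4e is headed as doses, and the per-capsule qualifier directly follows the 25 mg figure. It could be read as applying to 25 mg only, which would match the main text, with 10 mg then being the session dose. This is the less natural reading, but the wording does not exclude it. What stands, therefore, is that the text is wrong or ambiguous. A reader might infer that one instruction must be false, and that goes too far.

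The second reply is that the 20 mg case is remote. Staff would have to dispense two capsules each labelled 10 mg for a session whose prescription and case report form both say 10 mg, past a labelled bag, a co-signed prescription and a logged dose. A reader might infer that participants are likely to receive a double dose. The documents do not support that: the total is consistent throughout, and they give no probability of error. This reply also stands.

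Third, the two sources are not equally reliable. The main text is the specific administration instruction and gives both count and strength. Appendix III has other details that do not fit this trial. Item D.1c allows session numbers 1 to 4 although there are two drug sessions, and section C calls the study single-blinded although it is a single-group, fixed-dose trial. This points to B.4e as the likelier slip, without proving it.

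Finally, staff have other references. Item C.3g requires an on-site binder covering dosage, preparation and administration, and A.6c records the dosage form received. The prescription form, the order record and the drug master files are not among the documents, and any of them may state the strength. That lowers the practical risk but leaves the conflict in the text.

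**Conclusion.** Wrong as written, and minor. This is an internal inconsistency in the drug-handling instructions: the low-dose capsule is 5 mg in the main text and, on the natural reading, 10 mg in Appendix III B.4e, a factor of 2. The listed prescription content does not resolve it.

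The 20 mg and 5 mg figures bound what crossing the instructions with a single slip would produce. They are conditional on staff combining the two despite the checks, and they are not a forecast. The conclusion assumes that the per-capsule qualifier covers both strengths; if it covers only 25 mg, the fault is ambiguity and not contradiction. The supplied strength cannot be determined from the documents, though 5 mg is likelier.

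The outcomes, sample size, eligibility and analysis are untouched. The point deserves correction because it concerns a figure that staff rely on at a step with a safety purpose.

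**What to change.** Establish the supplied capsule strength first. Appendix III A.2 already provides the source: "A record of the request for investigational drugs from the manufacturers will be kept in the study's file as reference". The supplier can confirm it if the record does not. Then state it the same way everywhere.

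- **If the capsules are 5 mg (likelier):** change B.4e to '5 mg or 25 mg psilocybin (per capsule)', and have D.1d specify '10 mg as two 5 mg capsules (session 1) or 25 mg as one 25 mg capsule (session 2)'. The same edits serve if B.4e was meant to give 10 mg as the session dose.
- **If the capsules are 10 mg:** change the administration paragraph of the General Investigational Plan to one 10 mg capsule, and have D.1d specify '10 mg as one 10 mg capsule (session 1) or 25 mg as one 25 mg capsule (session 2)'.

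Either version gives exactly 10 mg and then 25 mg (2 × 5 or 1 × 10, then 1 × 25). The cost is one confirmation, two short wording changes, a minor resubmission, and relabelling of any stock already labelled with the wrong strength.

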Appendix IV. Security Provisions for Drug Storage

Building Level Security: CHS- Center for Health Sciences, SEMEL Institute

[name]

Building access is restricted by swipe access at the building entrance 7:00 PM- 6:00 AM. Our General Laboratory resides on the A floor in the 8-wing (i.e., south corridor) of the UCLA Semel Institute.

Laboratory Level Security

Business hours are 8am - 7pm and doors to the General Laboratory are maintained locked outside of business hours. A waiting room (room A8-216) at the entrance of the general laboratory is staffed by a UCLA Health administrator during business hours who monitors the entrance to the general laboratory. The waiting room also has security camera that records all activity at the entrance of the laboratory 24/7. The security camera is monitored by UCLA CHS security.

Storage Room Security

The drug storage room (A8-259) is located towards the very back of the laboratory space and is maintained locked at all times. Within the drug storage room, the controlled substances will be locked in a Hollon burglar safe (ID/Serial#: B2015E). The burglar safe is made with steel construction, 4 solid steel active locking bolts, a drill resistant hard plate and a UL listed Type 1 Securam Audit Trail digital lock. The safe is anchored to the floor with 4 bolts. The dimensions of the safe are 20" H x 15" W x 15" D

Controlled Substances Program Usage Log

Principal Investigator: _____

Purchase Order		Date Received	Initial Volume Received	Container ID:
Drug Information				
Lot			Expiration Date	

[illegible]

FINAL DISPOSITION	
 CS remaining balance zero Container deface and disposed	 Remaining unused CS item relinquished Contact EH&S CS Program for disposal of remaining CS. Submit request via E-mail to: [contact]

[illegible]
